#### Procedures and Methods:

*Intervention content.* I am currently in the process of building an initial draft of the intervention in Qualtrics to prepare for formative development. The intervention has three features (see Appendix 2): depression symptom and mood monitoring designed to increase engagement (i.e., treatment initiation), practical support (i.e., appointment reminders), and emotional support (i.e., encouraging messages). Symptom monitoring will be accomplished through repeated assessment of depression symptoms with the PHQ9 (with the exception of the suicide item which will be excluded in concordance with IRB approved protocols in the past). Mood will be monitored using a mood adjective list composed of 7 positive mood adjectives (talkative, enthusiastic, confident, cheerful, energetic, satisfied, and happy) and 7 negative mood adjectives (tense, anxious, distracted, restless, irritated, depressed, guilty). Specifically, participants will be asked to report on the PHQ9 (except the suicide item): 1. The 8 depressive symptoms by rating each one in turn from 0 to 3 (0 "none of the time", 1 "less than half the time", 2 "more than half the time", 3 "most or all of the time", in the past 24 hours). They will also be asked to rate the 14 different adjectives on an analog scale of 0-100. Finally, they will be asked whether anything has happened since the last report to trigger a symptom change (both positive and negative events). Patients will be asked to report how important, expected, pleasant, unpleasant, and stressful this event was on an analog scale of 0-100. Assessments will be completed through online surveys. Practical support will consist of reminders of upcoming mental health appointments. Emotional support will be encouraging messages thanking patients for reaching out and prioritizing their mental health needs. A list of possible messages will be created as a result of our interviews with our patient and provider stakeholders. Practical and emotional support messages will be delivered through push texts (i.e., texts that don't require a response).

*Intervention programming.* The intervention will use a daily diary assessment procedure and is programmed using an electronic platform, i.e. Qualtrics. Qualtrics is approved by VA central office for research use. Qualtrics

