has an ATO agreement for use for government data collection as it is the only Experience Management Platform with FedRAMP authorization, ISO 27001 certification, and FISMA compliance. The intervention will be on a set schedule to deploy once a day in the evening when patients would receive a text prompt to respond to questions described in the prior section which is estimated to take 5-10 minutes, or patients may receive a push text message with information only (practical or emotional support). Qualtrics has the capacity to automatically deploy contact information for the patient's provider when respondents' depression score is elevated beyond a clinical cut-off point of 15 (indicative of moderately severe depression which likely warrants treatment for depression using antidepressant, psychotherapy, or a combination of treatments).

**Phone screening.** Veterans interested in participating will initially contact the study research assistant (RA) by phone and participate in a phone screen for eligibility. Alternatively, an RA will be checking for new mental health referrals to the mental health clinic and contact patients, initially via mail and later by phone per VA approved procedures. The screening interview was developed and used at USF for screening participants for NIH funded grants and the PI's dissertation. The interview will assess for inclusion and exclusion criteria in Table 2. Veterans who are eligible following the phone screen will be invited to a face-to-face session. Veterans will be informed that study participation does not affect their usual mental health care. Patients that present with mental health emergencies will be screened with the CSSRS per VA policies and VA police will be contacted if patient is deemed to need emergency care.

**Data collection.** Informed consent. The initial face-to-face session will include answering questions, addressing concerns, and administering written informed consent. After written informed consent, participants will be enrolled in the study and qualitative interviews will be performed when a draft of the intervention is tested.

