#### **A4c. Aim 3.**

**Study/Design Overview:** Aim 3 will focus on completing phase 2 of the eHealth intervention development, which will be a formative evaluation. For this portion of the study we will collect both qualitative and quantitative data from a new sample of patients using same inclusion/exclusion criteria in Table 2. This portion of the study will help to determine usability, acceptability, engagement with the intervention, and potential problems with completing the intervention and collecting data in a complete and rigorous manner.

Participant recruitment and sampling: Participant recruitment and sampling will follow steps described in Aim 2. The sample size selected for this aim (n=15) is in line with samples recommended for formative evaluations and pilots. The sample is attainable based on rationale presented in Aim 2. The analytical rationale for the sample size is based on the proposed analyses presented below.

Procedures: Veterans recruited for this aim will be asked to complete 1) baseline questionnaires to understand the clinical make-up of the sample and unobserved patient characteristics that may impact our formative evaluation findings, 2) the intervention, and 3) a semi structured interview to complete the formative evaluation.

Self-report measures: These quantitative measures will be used to better understand the makeup of our sample in terms of clinical characteristics and treatment readiness that may not otherwise be observable from the structured data in their EHRs: **Patient Health Questionnaire 9 (PHQ-9)**, 9-item instrument that assesses the symptoms of depression corresponding to the Diagnostic and Statistical Manual Version 5 (DSM-5) diagnostic criteria for a major depressive episode. Item responses are on a four-point scale (from occurring “not at all” to “nearly every day” over the past two weeks) resulting in a score range from 0 to 27. The PHQ-9 has similar psychometric properties to other measures of depression. PHQ-9 is favored for its brevity and ease of use in clinical settings (Cameron et al, 2011).

**Posttraumatic Stress Disorder Check List for DSM-5 (PCL-5)**, 20-item self-report of the severity of PTSD symptoms in the past month using a 5-point scale (0-4), ranging from “Not at all” to “Extremely.” A cut-point of 50 (range 0-80) represents a probable diagnosis of PTSD.

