Participants will respond on a 5-point scale ranging from not at all confident to very confident. This scale has high internal consistency with Cronbach's alpha of .94-.96. This scale will provide data on patient post-intervention self-efficacy.

**Acceptability of intervention:** Rate of agreement to participate and study enrollment factors.

**Engagement in intervention:** Percentage of prompts completed/participation days. Other outcomes will be extracted as themes from our analyses of semi-structured interviews.

Intervention: Patients will receive text prompts once a day on their own phones with a Qualtrics survey link (see

Appendix 2 and detailed description of intervention content in Aim 2). Participants will receive feedback on how their depression score compares to a nationally representative average extracted from MIDUS (Midlife in the United States: A national epidemiological study of health and well-being), data which we already have and used for publication ([name], [name], et al, 2018; [name], [name], under review).

Quantitative Analyses:

**Data processing.** Data will be checked for out of range values and missing data where appropriate through

plotting and descriptive analyses. Finally, data will be transformed as needed to create the variables of interest (e.g. age of depression onset as age of first episode visible in the EHR).

**Missing Data Strategies.** We will minimize the level of missing data (due to loss to follow-up, withdrawal, or missing assessments) to the extent possible. If missing data occur, I will work with [name] to assess the missing data mechanism for data missing due to loss to follow-up or withdrawal. I will compare baseline measures (e.g.,

demographics, clinical history, etc.) between subjects that have complete outcome data and those that do not

using logistic regression. Multiple imputation will be used for missing data in conjunction with a pattern of missingness. Missing data will be evaluated on an ongoing basis and recruitment may be continued beyond the original sample to achieve the desired power for the proposed analyses.

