*Data Analysis. First, descriptive analyses will be performed on all baseline patient characteristics extracted for all patients approached for study enrollment, including those who agreed and did not agree to participate. To compare these two groups, we will use student t-tests (for continuous variables) and chi-square analysis (for categorical variables). This information will be used to derive acceptability of the proposed intervention. Next, descriptive analyses will be performed on the baseline questionnaires collected from the group of participants enrolled. This will give us additional data about patient characteristics that may further refine our phenotypes or improve study feasibility in the future. Engagement will be derived from percentage of prompts completed per days of participation in the intervention. Finally, we will calculate rates of treatment initiation (and corresponding 95% confidence interval) and compare to the initiation rate identified in our recent study on the Aim 1 cohort. To compare study treatment initiation to rates observed in Aim 3 to those in Aim 1 sample we will calculate the 95% confidence interval (CI) for the difference score between proportions (see Franklin, 2007). A significant difference will be denoted if the 95% CI does not include zero (Cumming & Finch, 2005). I will use negative binomial regression which accounts for overdispersion if treatment initiation is low (Coxe, West, & Aiken, 2009).*

Qualitative interviews and analysis: The interviews will be conducted using a semi-structured interview guide (see Appendix 3) and the same methods as Aim 2 interviews and analysis. These interviews will focus on the user's experiences using the self-monitoring intervention. Feedback will be sought about the functionality of the intervention, its perceived use, and ways to enhance it. We will specifically inquire about patients' perceptions about the three parts of the intervention: the symptom self-monitoring, practical support (i.e., appointment reminders), and emotional support (i.e., encouragement). Patients will also be asked to provide suggestions for emotionally supportive messages patients may want to see as they prepare to attend mental health sessions. Qualitative data will be analyzed in the same manner as presented in Aim 2.

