An eHealth intervention to increase depression treatment initiation and adherence among veterans referred for mental health services (CDA 18-189)

NCT05990075

November 30, 2022

*Analysis plan:*

*Data processing.* Data will be checked for out of range values and missing data where appropriate through plotting and descriptive analyses. Finally, data will be transformed as needed to create the variables of interest (e.g. age of depression onset as age of first episode visible in the EHR). *Missing Data Strategies.* We will minimize the level of missing data (due to loss to follow-up, withdrawal, or missing assessments) to the extent possible. If missing data occur, I will assess the missing data mechanism for data missing due to loss to follow-up or withdrawal. I will compare baseline measures (e.g., demographics, clinical history, etc.) between subjects that have complete outcome data and those that do not using logistic regression. Multiple imputation will be used for missing data in conjunction with a pattern of missingness. Missing data will be evaluated on an ongoing basis and recruitment may be continued beyond the original sample to achieve the desired power for the proposed analyses. *Data Analysis.* First, descriptive analyses will be performed on all baseline patient characteristics extracted for all patients approached for study enrollment, including those who agreed and did not agree to participate. To compare these two groups, we will use student t-tests (for continuous variables) and chi-square analysis (for categorical variables). This information will be used to derive acceptability of the proposed intervention. Next, descriptive analyses will be performed on the baseline questionnaires collected from the group of participants enrolled. This will give us additional data about patient characteristics that may further refine our phenotypes or improve study feasibility in the future. Feasibility will be derived from percentage of prompts completed per days of participation in the intervention. Finally, we will calculate rates of treatment initiation (and corresponding 95% confidence interval) and compare to the initiation rate identified in the literature. To compare study treatment initiation to rates we will calculate the 95% confidence interval (CI) for the difference score between proportions (see Franklin, 2007). A significant difference will be denoted if the 95% CI does not include zero (Cumming & Finch, 2005).

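### Does dividing completed prompts by days of participation hide patients who abandon the intervention?

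*SAP*

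**What the plan says.** The SAP's data-analysis paragraph states: "Feasibility will be derived from percentage of prompts completed per days of participation in the intervention". The corresponding sentence in Protocol A4c (Aim 3, Data Analysis) differs only in its label: "Engagement will be derived from percentage of prompts completed per days of participation in the intervention". The Aim 3 outcome list gives the short form: "Percentage of prompts completed/participation days".

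On contact frequency, Aim 3 states: "Patients will receive text prompts once a day on their own phones with a Qualtrics survey link". The Aim 2 description of the intervention adds texts that need no reply: "Practical and emotional support messages will be delivered through push texts". Its programming paragraph allows such a text to be sent in place of the survey prompt.

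No sentence fixes the number of intervention days or says when a patient's participation ends. There are indirect cues. One self-efficacy item in Aim 3 looks two weeks ahead, another runs until the therapist is seen, and the background (A1, Gaps Addressed) describes support from referral until treatment begins. Appendix 2 is cited for the intervention but was not among the documents available.

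**The concern.** Engagement is one of the questions Aim 3 is meant to answer: "This portion of the study will help to determine usability, acceptability, engagement with the intervention". The intervention exists to keep people from disengaging while they wait for care, so a measure that cannot register abandonment would be a poor fit. The SAP itself expects incomplete data "due to loss to follow-up, withdrawal, or missing assessments".

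If a patient's days stop accruing at the moment of quitting, the lost days leave the numerator and the denominator together. The pilot could then report a high completion figure while a third of the patients had left, and that figure might be carried into the planning of the later randomised trial. The applicant's own diary studies, cited in support of feasibility, ran 3 to 7 days, so they say little about persistence over a longer wait.

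**Working it through.** The plan states no target, expected completion rate or drop-out rate for this measure, so there is no figure to reproduce. The check asks how far the readings can diverge.

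**Inputs from the documents:** N = 15 patients (Aim 3 sample size); one survey prompt a day.

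**Inputs assumed:** window T = 14 days; answer rate while active s = 0.70, the same for everyone; q patients quit after day d.

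**Formulas**
- Active days: A = (N − q)·T + q·d
- Prompts completed: C = s·A
- Reading 1, participation ends at quitting: C / A = s, whatever q and d are
- Reading 2, silent days still count: C / (N·T)
- Difference: s·q·(T − d) / (N·T)

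**Results, T = 14, s = 0.70**

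| Quitters | Active days | Completed | Reading 1 | Reading 2 |
|---|---|---|---|---|
| none | 210 | 147 | 70.0% | 147/210 = 70.0% |
| 1 after day 7 | 203 | 142.1 | 70.0% | 142.1/210 = 67.7% |
| 3 after day 7 | 189 | 132.3 | 70.0% | 132.3/210 = 63.0% |
| 5 after day 4 | 160 | 112 | 70.0% | 112/210 = 53.3% |
| 8 after day 4 | 130 | 91 | 70.0% | 91/210 = 43.3% |

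**Sensitivity, five quitters after day 4**
- s = 0.50: 0.50 × 5 × 10 / 210 = 11.9 points
- s = 0.90: 0.90 × 5 × 10 / 210 = 21.4 points
- T = 28, s = 0.70: 0.70 × 5 × 24 / 420 = 20.0 points

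These are scenarios, not bounds. Eight quitters in the table already give 70.0 − 43.3 = 26.7 points.

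**Information-only days.** Suppose days 7 and 14 carry only a text needing no reply, and those days are counted as participation. Each patient then has 12 survey prompts, or 180 in all. With no quitters the ratio is 0.70 × 180 / 210 = 126/210 = 60.0%, against 126/180 = 70.0% of survey prompts, so the ratio now understates completion. The protocol separates these texts from survey prompts, so an analyst would not normally count them. The example shows only that the wording does not fix even the direction of the difference.

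**What the data allow.** Each response is a dated survey return. A, C and N·T can all be formed from those returns, the enrolment date and the end of the intervention period. Neither reading requires anything extra to be collected from patients.

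**The case for a change.** The strongest case for a change is that the same responses can give 70% or 53%, that no separate retention rate is listed as an outcome, and that a sentence or two written now would prevent the denominator from being chosen after the results are seen. The planned multiple imputation does not settle the matter: it is not tied to this ratio, and an unanswered prompt is itself the outcome rather than a missing value.

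Much of this stands. The arithmetic is right, the documents contain no end rule, and a report giving only a while-active rate would be incomplete.

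It does not amount to a fault in the plan. One reading shows no difference at all, and nothing in the text selects the unfavourable one. Drop-out is also visible elsewhere: the missing-data paragraph calls for examining loss to follow-up and withdrawal and for comparing patients with and without complete outcome data. Aim 3 also sets out to learn what problems patients have in completing the intervention and interviews them about using it.

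A prescribed denominator would need an end date that the documents do not set for this measure. The first mental health visit, an obvious candidate, need not coincide with treatment initiation as Aim 1 defines it, since that definition includes primary care encounters and leaves out assessments.

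**Conclusion.** No change is called for. The plan leaves a counting rule unwritten for a descriptive measure in a 15-patient formative pilot. No threshold, hypothesis test or go/no-go decision depends on it, and the treatment-initiation comparison is unaffected. An analyst reporting engagement would ordinarily state the denominator, leave out texts that need no reply, and show how many patients stopped and when. The data already planned support all of that.

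The difference between readings is zero with no quitters and 16.7 points in the five-quitter, 14-day, 70% scenario. It grows with more quitters, earlier quitting, a longer window or a higher answer rate. All of those inputs except the 15 patients and the daily prompt are assumptions. The use of engagement in the protocol and feasibility in the SAP for the same ratio is a clerical inconsistency and does not alter what is computed. This conclusion is limited to the text available; Appendix 2 may already give the intervention's length.
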